3.2.2 Pharmacokinetic variables

Two PK samples will be obtained at steady state from at least 20 patients to determine the population pharmacokinetics of ceftaroline fosamil, ceftaroline, and ceftaroline M-1 in this patient population. If CSF sample collection is expected per standard of care, PK blood samples should be collected at the time of CSF collection as a matching sample (see section

5.4.1 of the protocol). The total number of PK blood samples will not exceed 2. After the 2 PK blood samples have been collected, any portion of a CSF sample (collected as part of standard of care) not required for the patient's medical care should be retained for PK analysis.

Pharmacokinetic variables include actual sample collection times and plasma concentrations of ceftaroline fosamil, ceftaroline, and ceftaroline M-1 at each time point. If available, concentrations of ceftaroline and ceftaroline M-1 in cerebrospinal fluid (CSF) will be reported.

Plasma concentrations of ceftaroline fosamil, ceftaroline and ceftaroline M-1 will be listed by age cohort.

Covance Laboratories, using appropriate bioanalytical methods will determine plasma concentrations of ceftaroline fosamil, ceftaroline, and ceftaroline M-1.

3.3.1 Demographic and baseline characteristic variables

3.3.1.1 Demographic variables

Demographic variables include age (days), sex, race, and ethnicity. Age (days) will be calculated as (date of informed consent - date of birth + 1).

3.3.1.2 Surgical and medical history variables including antepartum/ peripartum period

Surgical history variables include procedures, study day of procedure start date, and current medication yes/no. Medical history variables include diagnosis, study day of condition start date and duration of condition (see [Section 3](#) for calculation of study day and duration), status (past or current), and any current medication yes/no. Surgical and medical histories will be coded using MedDRA Version 12.0 or higher.

3.3.1.3 Baseline microbiological assessment variables for blood, CSF, urine, and other specimens

Identification of pathogens and susceptibility results will be recorded by both the local microbiology laboratory and the central reference laboratory. The identification and susceptibility results of the central microbiology reference laboratory will be regarded as definitive, if after re-testing, any discrepancies noted are not resolved. In the circumstance that the central lab could not isolate any organism from the submitted specimen, the local lab result will be used for organism identification (not including a result of "No Growth" at the central laboratory, which should be reported).

Microbiological assessments at baseline include collection data, culture data, antibiotic susceptibility data, and gram stain data:

- Collection data: specimen collected yes/no, type of specimen, reason for no specimen, specify if attempt made but unable to obtain, collection date and time and specimen acquisition method

- Culture data: specimen work up performed by, culture outcome, culture source location, laboratory name and identifier, pathogen type, isolate identification, isolate classification, isolate quantitation for 1 µL, 5 µL, 10 µL plates (for urine specimens only), isolate sent to central lab yes/no, reason if no specimen sent to central laboratory, accession identifier primary and secondary
- Antibiotic susceptibility data: local susceptibility tested yes/no, isolate identification, antibiotics tested, susceptibility, susceptibility criteria and susceptibility method
- Gram stain data: gram stain done yes/no, specify if no gram stain done and gram stain results, for example, epithelial cell results, etc.

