5.2. Microbiological assessments

5.2.1. Blood sample for culture

If clinically indicated and performed as part of patient's regular medical care, obtain blood for culture at Baseline (preferably before any antibiotics are administered) and at any time through TOC. Cultures should be repeated per standard of care upon knowledge of a positive result until sterilization is confirmed. Perform culture and organism identification at the local or regional laboratory, as applicable. Send all isolates to the central laboratory for organism identification and susceptibility testing.

Refer to the study-specific clinical and microbiology laboratory manual for specific procedures pertaining to the collection, processing, storage, and shipment of blood culture or isolates.

This protocol complies with European Union's recommendations for blood loss associated with pediatric research³ and the World Health Organization guidelines "Blood Sample Volumes in Child Health Research: Review of Safe Limits".⁶ To minimize risk from blood loss associated with this study, standard of care laboratory results will be used whenever possible. All safety laboratory tests will be limited to local processing. In addition, pediatric blood collection tubes will be used and capillary method of blood draw will be implemented whenever feasible. PK samples will be collected from patients unless deemed unsafe due to the risk from additional blood loss (per the investigator's judgment).

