8.4.2. Microbiological response definitions

8.4.2.1. Microbiological Outcome at Test-of-Cure

The per-pathogen microbiological outcome categories at EOT and TOC are defined in [Table 6](#). Favourable microbiological outcomes are eradication or presumed eradication. Per-patient microbiological response at EOT and TOC will be determined programmatically based on individual outcomes for each baseline pathogen. In order for a patient to have a favourable microbiological response, the outcome for each baseline pathogen must be favourable (eradicated or presumed eradicated). If the outcome for any pathogen is unfavourable (persistence or presumed persistence), the patient will be considered to have an unfavourable microbiological response.

Baseline pathogens will be determined based on central laboratory data. Rules for determination of pathogens will be described in the SAP.

Table 6 Per-pathogen microbiological outcomes categories at End of Treatment and Test-of-Cure

Microbiological Response ^a	Definition
Eradication	Source specimen demonstrated absence of the original baseline pathogen
Presumed eradication	Source specimen was not available to culture and the patient was assessed as a clinical cure
Persistence	Source specimen demonstrates continued presence of the original baseline pathogen
Presumed persistence	Source specimen was not available to culture and the patient was assessed as a clinical failure
Indeterminate	Source specimen was not available to culture and the patient's clinical outcome was assessed as indeterminate

a For patients who are clinical failures before TOC, the microbiological outcome will be carried forward to TOC and will be determined based on the cultures and/or clinical outcome at the time of the early clinical failure determination.

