3.2.1.2 Per-pathogen and per-patient microbiological response variables at EOT and TOC

The per-pathogen microbiological outcome categories for pathogens identified at baseline are defined in [Table 7](#). Local microbiology data will only be used when central data is not available, for example, samples were not sent to the central laboratory for processing. Please see [section 3.3.1.3](#) for further details.

Table 7 Per-pathogen microbiological response categories

Microbiological Response ^a	Definition	Response Category
Eradication	Source specimen demonstrated absence of the original baseline pathogen	Favorable
Presumed eradication	Source specimen was not available to culture and the patient was assessed as a clinical cure	Favorable
Persistence	Source specimen demonstrates continued presence of the original baseline pathogen	Unfavorable
Presumed persistence	Source specimen was not available to culture and the patient was assessed as a clinical failure	Unfavorable
Indeterminate	Source specimen was not available to culture and the patient's clinical outcome was assessed as indeterminate	Indeterminate

^a For patients who were clinical failures before TOC, the microbiological outcome will be carried forward to TOC and will be determined based on the cultures and/or clinical outcome at the time of the early clinical failure determination.

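### A central-laboratory No Growth on a shipped isolate displaces a locally identified baseline pathogen, because SAP 3.3.1.3 takes it out of the local fallback without separating a dead isolate from a sterile specimen

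*SAP*

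**What the plan says.** Protocol 5.2.1 puts the primary blood culture at the site: "Perform culture and organism identification at the local or regional laboratory, as applicable". It then instructs: "Send all isolates to the central laboratory for organism identification and susceptibility testing". Sections 5.2.2 to 5.2.4 give the same shipping instruction for urine, CSF and other specimens.

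Protocol 8.4.2.1 sets the source for analysis: "Baseline pathogens will be determined based on central laboratory data". It leaves the detailed rules for determining pathogens to the SAP.

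SAP 3.3.1.3 has both laboratories record identification and susceptibility. The central result "will be regarded as definitive, if after re-testing, any discrepancies noted are not resolved". The fallback follows. It opens with "In the circumstance that the central lab could not isolate any organism from the submitted specimen" and continues: "the local lab result will be used for organism identification (not including a result of" *No Growth* "at the central laboratory, which should be reported".

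SAP 3.2.1.2, on microbiological response, states: "Local microbiology data will only be used when central data is not available". It gives samples that were never sent as an example and refers to 3.3.1.3 for detail.

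**The concern.** An isolate is an organism that has already grown. If the central laboratory cannot grow it again, the likely causes are loss of viability or handling in transit. The result says little about whether the infant was infected. As worded, however, the exception lets that result stand in place of the local positive.

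This also treats sites unevenly. A site that ships nothing keeps its local pathogen under SAP 3.2.1.2. A site that follows the protocol but whose isolate dies on the way loses it.

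The baseline pathogen decides membership of Micro-ITT (SAP 2.1.4), the baseline pathogen summaries (SAP 4.2.3), and the clinical and microbiological response tables by pathogen (SAP 4.2.7.1 and 4.2.7.2). It also feeds the MITT exclusion for resistant baseline pathogens (SAP 2.1.3). In a study of 24 infants the pathogen-positive group will be small, so one infant matters.

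**Working it through.** The plan gives no figure to reproduce. The check traces one case through the rules and then sizes it.

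**Tracing the case.** An infant has one baseline blood pathogen, identified locally. The isolate is shipped and the central laboratory reports no growth.

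1. Local and central results disagree, so SAP 3.3.1.3 calls for re-testing. Re-testing cannot revive a dead isolate. Neither document provides for a repeat shipment or says what to do with a non-viable isolate.
2. The discrepancy stays unresolved, so the central result is definitive.
3. The fallback would apply, because the central laboratory isolated nothing. The parenthesis then removes *No Growth* from it. The two outcomes are not defined separately, so two programmers could take different branches for this infant.
4. SAP 3.2.1.2 does not clearly help: a *No Growth* can be counted as available central data. Protocol 8.4.2.1 also points to the central result.
5. On the plain reading the infant has no baseline pathogen. The infant leaves Micro-ITT and the by-pathogen tables. With a second confirmed pathogen, the infant would stay in Micro-ITT and lose only the one entry.

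**Size.** The inputs are the Jeffreys two-sided 95% interval (SAP 4.2.7.2) and two assumptions the documents do not supply: the number n of pathogen-positive infants, and the rate r at which a shipped isolate is non-viable, taken as one per infant and independent.

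Share lost per infant = 1/n: 1/4 = 25.0%, 1/8 = 12.5%, 1/12 = 8.3%.

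Chance of losing at least one = 1 − (1 − r)^n. For n = 8 and r = 5%: 1 − 0.95^8 = 33.7%.

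| n | r = 2% | r = 5% | r = 10% |
|---|---|---|---|
| 4 | 7.8% | 18.5% | 34.4% |
| 8 | 14.9% | 33.7% | 57.0% |
| 12 | 21.5% | 46.0% | 71.8% |

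Effect on the favourable rate, assuming one unfavourable response among n. The interval comes from the Beta(x + 0.5, n − x + 0.5) quantiles, with the upper limit set to 100% when x = n.

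| n | Local positive kept | Unfavourable infant lost | Favourable infant lost |
|---|---|---|---|
| 4 | 3/4 = 75.0% (28.4–97.2) | 3/3 = 100% (46.4–100) | 2/3 = 66.7% (17.7–96.1) |
| 8 | 7/8 = 87.5% (54.6–98.6) | 7/7 = 100% (70.8–100) | 6/7 = 85.7% (49.9–98.4) |
| 12 | 11/12 = 91.7% (67.2–99.1) | 11/11 = 100% (80.0–100) | 10/11 = 90.9% (64.7–99.0) |

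The estimate can move either way. The larger shift comes from losing the one unfavourable case.

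**The case against.** **The parenthesis can be read differently.** It could mean that *No Growth* is reported alongside the local identification. That reading is possible but less natural, and SAP 3.2.1.2 and Protocol 8.4.2.1 lean against it. If it is what was meant, the sentence still needs rewriting, because the text does not settle which branch applies.

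**Not everything shipped need be an isolate.** Protocol 5.2.1 also mentions shipment of blood culture, and SAP 3.3.1.3 speaks of a submitted specimen. A central *No Growth* on primary material can be a true result, and the exception may have been written for that case. The shipping details sit in laboratory manuals outside these documents. This part of the objection stands: a rule that overrode every central *No Growth* would go too far.

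**Re-testing is a safeguard.** It is, and the problem is limited to discrepancies that survive it. A dead isolate is the kind that would.

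**Central precedence is the protocol's choice.** That is so, and any exception should be declared as one.

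**The MITT effect is uncertain.** SAP 2.1.3 does not say which laboratory establishes resistance, and the local fallback covers identification only. Infants whose infection is known at entry to be resistant to the combination are already ineligible (Protocol 3.2, criterion 2). The effect is possible but not shown.

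**Conclusion.** The concern holds for shipped isolates that give no growth after re-testing. Following the rule as written would produce a wrong Micro-ITT set and wrong by-pathogen tables by one infant per event, or 1/n of the group. The values of n and r are assumptions, so the tables above are illustrations and do not predict how often this happens.

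A reader might infer three stronger points that the documents do not support:

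- **That the same rule turns persistence into eradication after baseline.** The exception sits in a baseline section. SAP 3.2.1.2 cross-refers to it, but SAP Table 7 defines eradication by the source specimen showing that the pathogen is absent, and in this case the source specimen grew it. No text makes a dead follow-up isolate count as eradication.
- **That the local finding disappears.** It is lost from the analysis variable only. Local results are recorded (SAP 3.3.1.3), and baseline culture data are listed (SAP 4.2.3).
- **That the trial's main conclusion is at risk.** The primary objective is safety, no hypothesis is tested, and clinical cure is also tabulated in ITT and MITT. The primary safety analysis and the sample size are unaffected.

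This should be corrected, but it is confined to secondary microbiological results.

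**What to change.** In SAP 3.3.1.3, replace the parenthesis with a rule that depends on what was shipped:

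- If a locally identified isolate sent to the central laboratory yields no growth after re-testing, the local identification, and local susceptibility where available, defines the baseline pathogen and is flagged. The central *No Growth* is shown in the listing.
- If primary specimen material was submitted, a central *No Growth* remains the result.

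Align SAP 3.2.1.2 so that a no-growth result on a shipped isolate counts as central data not available. Note in the SAP that this is an exception to Protocol 8.4.2.1.

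The cost is a few sentences and one flag. SAP 3.3.1.3 already lists the local identification, the local susceptibility and whether an isolate was sent, so no new data collection should be needed. The downside is that a few flagged pathogens will rest on local identification without a central ceftaroline MIC, so they may still be missing from the by-MIC table. A footnote should give their number.

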3.3.2 Definition of prior and concomitant medication

Any medications (non-antimicrobial, antimicrobial, parenteral nutrition and blood/blood-component transfusions) taken by the patient between 7 days prior to study entry (or taken by the lactating mother of breast fed patients within 3 days prior to study entry) and prior to the first dose date of study therapy received will be considered prior medication. Any medication taken by the patient (or by the lactating mother of breast fed patients) at any time between dates of the first dose (including the date of the first dose) of study therapy through the TOC visit, inclusive, will be considered concomitant medication. Any medication started prior to the study entry and ended/ongoing up to the TOC will be considered as both prior and concomitant medication.

If any medications reported are not able to be determined as prior medications or concomitant medications due to missing or partial start dates and/or stop dates, the following imputation rules will be implemented:

- If the year is present but the month and day are missing, then 01JAN will be imputed for the start date and 31DEC for the stop date.
- If the year and month are present but the day is missing, then 01 will be imputed for the start date and the last day of the month for the stop date.

If both stop/start years are missing or both stop/start dates otherwise cannot be imputed, then the date will be treated as missing and the medication will be treated as both prior and concomitant medications.

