4.1.1.3. Microbiological assessments

Microbiological assessments should be performed preferably before any antibiotics are administered.

- If clinically indicated and performed as part of patient's regular medical care, obtain blood and urine samples for testing per [Section 5.2.1](#) and [5.2.2](#), respectively; cultures should be repeated per standard of care upon knowledge of a positive result until sterilization is confirmed
- If clinically indicated and performed as part of patient's regular medical care, obtain CSF or other specimens/tissue samples per [Section 5.2.3](#) and [5.2.4](#), respectively; cultures may be repeated per standard of care upon knowledge of a positive result.
- Obtain any prior microbiological and clinical data (eg, notes in medical records confirming worsening of signs and symptoms of sepsis) that may help determine eligibility ([Section 5.2](#))

Enrol the patient and assign to PK schedule after verifying that the patient meets all inclusion and no exclusion criteria. There should be no medically inappropriate delay in administration of study therapy.

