7.7. Concomitant and other treatments

All prior medications (taken or received within 7 days before the first dose of study therapy) and all concomitant medications (taken during the study), including, but not limited to, all antimicrobials, parenteral nutrition, and blood and blood-component transfusions will be documented. For patients who are being breast fed, all medications taken by the lactating mother for 3 days before first dose of study therapy through SFU will also be recorded.

Concomitant antibacterial therapy is not permitted except in the case of clinical failure.

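### SAP 3.3.2 separates prior from concomitant drugs at the calendar date of the first dose, so drugs used only in the hours before dosing on that date generally drop out of the prior-medication tables

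*SAP*

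**What the plan says.** SAP 3.3.2 sets three rules.

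1. **Prior.** The look-back opens "between 7 days prior to study entry", and use "prior to the first dose date of study therapy received will be considered prior medication".
2. **Concomitant.** This is use "at any time between dates of the first dose (including the date of the first dose) of study therapy through the TOC visit".
3. **Both.** "Any medication started prior to the study entry and ended/ongoing up to the TOC will be considered as both prior and concomitant medication".

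None of the three uses clock time. The imputation rules that follow deal with incomplete dates only. SAP 4.2.4 tabulates concomitant and prior drugs by ATC group and generic name in the Safety Analysis Set. It adds a table of the duration of prior drugs in the ITT set and lists both kinds by patient. For the definitions it points to SAP 3.3.3, which covers exposure and compliance, so no other rule refines 3.3.2.

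The protocol anchors prior medication on the dose, not the date. Section 7.7 counts drugs "taken or received within 7 days before the first dose of study therapy", and section 4.1.1.1 does the same.

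**The concern.** The SAP's date boundary and the protocol's dose boundary differ over the hours of the first-dose date that precede the first infusion. In late-onset sepsis those hours matter. Protocol 1.2 stresses starting antibacterials without delay, baseline may span the 36 hours before the first dose, and the exclusion criteria do not limit earlier antibacterials. The protocol also foresees antibiotics before study procedures, since it states only a preference: "Microbiological assessments should be performed preferably before any antibiotics are administered".

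The prior-medication tables are the planned summary of pretreatment in a single-arm study that reports cure rates, so a reader will use them to judge how much antibiotic cover infants already had. The concomitant table is read against a prohibition: "Concomitant antibacterial therapy is not permitted except in the case of clinical failure". A permitted pre-dose antibiotic shown there can be mistaken for something else. The SAP's adverse-event rule (3.1.1.1) already splits at the start of the first administration, so the medication rule is also out of line with the SAP itself.

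**Working it through.** The plan states no figure that depends on this rule, so there is nothing to reproduce beyond 3 × 8 = 24 infants. The check is to run example drug courses through the SAP's sentences and compare the result with a split at the start of the first dose.

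**Set-up (assumed for illustration).** First dose on day 0 at 14:00. Study entry, which SAP 3.3.2 does not define, is either day 0 at 09:00 or day −1 at 18:00. The third sentence has two readings. The literal one covers a drug that ended at any time up to TOC. The narrow one covers a drug that continued until TOC.

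| Course | Sentences 1 and 2 | With sentence 3 read literally | Split at start of first dose |
|---|---|---|---|
| Single dose, day −5 | prior | both | prior |
| Day −3 to day −1, finished | prior | both | prior |
| Single dose, day −1 22:00 | prior | both if entry is day 0; prior if entry is day −1 | prior |
| Day −1 06:00 to day 0 06:00, finished | both | both | prior |
| Single dose, day 0 06:00 | concomitant only | both if entry is day 0 at 09:00; otherwise concomitant only | prior |
| Single dose, day 0 11:00 | concomitant only | concomitant only | prior |
| Day −3 to day +2 | both | both | both |

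Under the narrow reading, all seven results equal the second column.

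- The 11:00 dose is lost from prior on every reading. The 06:00 dose is lost except where it precedes a same-day entry and the literal rule is applied by time.
- The course that ended at 06:00 on day 0 is labelled concomitant on every reading, though it finished eight hours before the first dose.
- The first two courses become concomitant only if sentence 3 is read literally. On that reading it contradicts sentence 2, which requires use on or after the first-dose date.

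**Size.** If k infants are affected in a given row, the row shifts by 100 × k/24 points overall, or 100 × k/8 within one cohort.

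- k = 1: 100/24 = 4.2 points overall; 100/8 = 12.5 points in a cohort.
- k = 3, spread over cohorts: 300/24 = 12.5 points overall.
- k = 6: 600/24 = 25 points overall.

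The documents give no value for k; these are assumed values to show the scale. An infant lowers the prior row only if the same drug was not also used on an earlier date within the look-back. An infant raises the concomitant row only if the drug was not also used after the first dose.

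**How often a pre-dose drug would fall on the first-dose date (illustration).** Assume one administration, uniformly timed over the w hours before the first dose, and a first dose at a uniformly distributed clock time. An administration h hours earlier falls on the same date with probability max(0, 1 − h/24). Averaging over h gives 1 − w/48 for w ≤ 24, and 12/w for longer windows.

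| w | Share on first-dose date |
|---|---|
| 6 h | 1 − 6/48 = 87.5% |
| 12 h | 1 − 12/48 = 75% |
| 24 h | 1 − 24/48 = 50% |
| 36 h | 12/36 = 33% |
| 7 days (168 h) | 12/168 = 7% |

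A simulation of one million draws agreed. The closer a drug is to the first dose, the more likely the date rule is to misplace it.

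**The case against.** Four arguments on the other side have force.

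**The protocol anchors only prior use at the first dose.** Section 7.7 describes concomitant drugs as those taken during the study, and consent precedes every study procedure. A drug given after consent but before dosing may therefore be concomitant under the protocol as well. This stands: the clear departure from the protocol is the loss from the prior tables. Counting such a drug as concomitant too is an inconsistency with the SAP's own first-dose boundary for adverse events.

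**The third sentence is ambiguous.** A reader might infer that antibiotics stopped days before the first dose will be tabulated as concomitant. The documents do not establish that. Read with the sentence before it, the third sentence can mean drugs carried through the treatment period, and drugs stopped on earlier dates then stay prior only. What stands is that two programmers could build different tables from the same text.

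**No key result uses these labels.** A reader might infer that mislabelled antibiotics would create protocol deviations, count as rescue or change the cure rate. They would not. Important deviations come from a separate guidance document and tracking system (SAP 2.2, 4.2.2). Clinical response rests on the investigator's assessment and the derivation in SAP Table 6. No analysis set uses prior or concomitant status, and the patient listings still show every drug. This stands in full.

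**Clock times may not exist for these drugs.** Protocol 7.5 records times for study infusions. Nothing says that the times of other drugs are collected. This stands and shapes the fix.

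**Conclusion.** The date boundary is a stated rule that gives wrong entries in the medication summary tables. A drug used only before dosing on the first-dose date is generally absent from prior and shown as concomitant, and a course that ended that morning is also shown as concomitant. The rule for drugs that are both prior and concomitant lacks a first-dose condition and needs rewording on either reading.

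Each affected infant is worth 4.2 points of 24, or 12.5 points of a cohort of 8. The number affected is unknown, and the timing shares above rest on assumed uniform times. The consequence is limited to how pretreatment and concomitant use are summarised. The primary safety analysis and the cure rates do not change. It is a modest point, but it should be corrected, because these tables are where a reader of a single-arm cure rate looks for earlier antibiotic cover.

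**What to change.** Redefine the categories in SAP 3.3.2 against the start of the first dose of study therapy:

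- **Prior:** any use in the 7 days before it. For drugs taken by a breast-feeding mother, use the 3 days before it, as in protocol 7.7. This also replaces the undefined study-entry anchor.
- **Concomitant:** any use at or after it, through the end of the period the SAP already sets.
- **Both:** started before it and continued at or after it. This replaces the third sentence.

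Use clock time where it was collected. Where the time of a drug on the first-dose date is missing, count the drug as both and give the number of such cases in a footnote. This matches the SAP's existing default for dates that cannot be resolved. It restores the prior count, but may still overstate concomitant use. In SAP 4.2.4, correct the cross-reference from 3.3.3 to 3.3.2.

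The cost is a few lines of SAP text, a date-time comparison in the derivation, and a residual category of both where times were not recorded. No new data are needed.
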